3 EXPERIMENTAL PLAN

3.1 STUDY DESIGN

This is a multicenter, randomized, double-blinded, placebo-controlled, 16-week, parallel group study. Subject eligibility will be based on inclusion and exclusion criteria described in Section 4. Approximately 314 eligible subjects will be randomized to study treatment in a 1:1 ratio. Subjects will be stratified based on Baseline 6MWD (≤ 350 meters and > 350 meters). Subjects will be treated with either inhaled treprostinil (6 mcg/breath) or placebo.

The study will consist of the following phases:

Screening Phase: Prospective subjects will undergo a screening evaluation within 30 days prior to the Baseline Visit (first dose of study drug). During this phase, eligible subjects will sign the informed consent form (ICF) and undergo screening assessments as described in Sections 7.1 and 7.3. The Screening and Baseline assessments may be combined if all entry criteria are satisfied within 48 hours prior to the first dose of study drug. Baseline PFTs and 6-minute walk test (6MWT) used to confirm eligibility criteria must be performed prior to randomization.

Baseline Visit: The Baseline assessments may be conducted over a 48-hour period prior to the first dose of study drug to allow for scheduling of all activities. Eligible subjects will undergo Baseline assessments (Sections 7.2 and 7.3), be assigned to a treatment group based on the randomization schedule, and receive the first dose of study drug (Day 1 is defined as the day the first dose of study drug is given). The Screening and Baseline assessments may be combined if all entry criteria are satisfied within 48 hours prior to the first dose of study drug. Baseline PFTs and 6MWT used to confirm eligibility criteria must be performed prior to randomization.

Treatment Phase: The Treatment Phase consists of 5 study visits to the clinic at Week 4, Week 8, Week 12, Week 15, and Week 16 (final study visit; at least 24 hours after the Week 15 Visit). Subjects will also be contacted at least weekly by telephone or email to assess subject tolerance to study drug, AEs, and changes to concomitant medications.

A schedule of visits and assessments is presented in Section 3.2.

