3.3.1.2 St. George's Respiratory Questionnaire

The SGRQ will be conducted at Baseline (prior to study drug) or as part of the Screening Visit assessment if the Screening and Baseline Visits are combined and at Week 16 (or ET for those subjects discontinuing study drug/study prematurely). The SGRQ should be completed as the first assessment during these visits (after informed consent is obtained) before the subject completes any of the other scheduled visit assessments. A copy of the SGRQ can be found in Appendix 15.3.

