3.3.2.2 Vital Signs

Vital signs will be assessed at Screening, Baseline, and each subsequent study visit or ET.

Vital signs measured will include blood pressure (systolic and diastolic), HR, respiratory rate

(RR), temperature, and weight. Height will be assessed at Screening only. Vital signs must be assessed following at least 5 minutes of rest (sitting) to ensure accurate measurement. No other measurements or procedures should be performed during this 5-minute period. When possible, vital signs should be collected prior to the 6MWT. If vital signs cannot be obtained prior to the 6MWT, they should be obtained after recovery of the 6MWT. Vital signs should also be assessed in the case of abnormal clinical signs and symptoms.

3.3.2.3 12-Lead Electrocardiogram

A 12-lead ECG will be recorded after at least 5 minutes of rest in the semi-recumbent position at Baseline (prior to study drug) and repeated at the Week 16 or ET Visit. Recordings should include lead II as a rhythm strip and contain at least 5 QRS complexes. ECG parameters to be collected include rhythm, HR, PR interval, QT interval, QRS duration, and any clinically significant abnormalities.

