### 8 GENERAL CONSIDERATIONS FOR DATA ANALYSES

All the data collected in the electronic Case Report Form (eCRF) will be listed. In general, listings will be sorted by treatment group, subject number, and scheduled assessment (if applicable). Listings will include assessment date, assessment time (if available), study day, and all relevant data collected in the eCRFs. For data collected on a fixed schedule, the assessment identifier or the nominal time point will also be included on the listing. Repeat or redundant observations within an assessment window and observations that do not fall within any predefined assessment window (and will, therefore, be excluded from summaries) will be flagged in these listings. Subjects who are not to be included in the analysis population (eg, Safety population, Per-protocol population) will be flagged.

In general, the data will be summarized by scheduled assessment (if applicable) within each treatment group. For continuous variables, summary statistics will include the mean, standard deviation, median, minimum, and maximum. For summaries of non-normal data such as 6MWD, interquartile range (lower quartile, upper quartile) may also be included. Minimums and maximums will be expressed using the level of precision in which the variable was collected. All other statistics will be rounded, using an additional decimal place than was collected. For discrete variables, summaries will include the frequency and percentage in each category. Percentages will be rounded to 1 decimal place. For all inferential analyses and descriptive comparisons, p-values will be rounded to 4 decimal places. Values less than 0.0001 will be denoted as <0.0001, and values greater than 0.9999 will be denoted as >0.9999 whenever practical, categories of discrete variables will be ordered and labelled as they appear in the eCRF, and all categories represented on the case report form will be included in summaries, even when they do not apply to any subjects in the study.

Unless otherwise specified, all statistical tests will be 2-sided at alpha level 0.05. All statistical calculations will be completed using SAS® Version 9.4 or above.

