### 8.6 ASSESSMENT WINDOWS

For any data summarized by scheduled visit, an analysis visit window will be used. The scheduled visits, as recorded on the eCRFs, and the corresponding target days and study day intervals are specified in Table 8-4. The analysis visit window will be derived based on the information specified in Table 8-4.

In the protocol, the visit window for Week 4, Week 8, Week 12, and Week 16 is  $\pm 5$  days and the visit window for the Week 15 visit is  $\pm 5$  days and at least 24 hours prior to Week 16 6MWT. In order to allow slotting of discontinuation visits and visits outside the planned schedule, the visit windows have been expanded for analysis purposes for Week 4, Week 8, Week 12, and Week 16. The nominal study visit identified as Week 15 in the eCRF will be used for the Week 15 visit provided it is at least 24 hours prior to Week 16 6MWT or there is no Week 16 visit.

Visit	Target Study Day	Study Day Interval
ECGs, SGRQ:		
Baseline	1	Study Day ≤1 (prior to the date of the first dose)
Week 16	113	1 < Study Day
PFTs, Clinical laboratory as	ssessments and NT-proF	BNP:
Baseline	1	Study Day $\leq 1$ (prior to the first dose)
Week 8	57	$1 < $ Study Day $\leq 71$
Week 16	113	99 < Study Day
Peak 6MWT:	·	
Baseline	1	Study Day ≤1 (prior to the first dose)
Week 4	29	$1 < $ Study Day $\leq 43$
Week 8	57	$43 < $ Study Day $\leq 71$
Week 12	85	$71 < $ Study Day $\leq 99$
Week 16	113	99 < Study Day
Trough 6MWT:		
Week 15	106	Nominal study visit and at least 24 hours prior to Week 16 6MWT or no Week 16 visit
Vital signs, Pulse oximetry:		
Baseline	1	Study Day $\leq 1$ (prior to the first dose)
Week 4	29	$1 < $ Study Day $\leq 43$
Week 8	57	$43 < $ Study Day $\leq 71$
Week 12	85	$71 < $ Study Day $\leq 99$
Week 15	106	Nominal study visit and at least 24 hours prior to Week 16 6MWT or no Week 16 visit
Week 16	113	99 < Study Day

 Table 8-4
 Assessment Windows for Scheduled Visits

Note: Study Day = (Assessment Date) - (First Dosing Date) +1

Abbreviations: 6MWT, 6-Minute Walk Test; ECG, Electrocardiogram; NT-proBNP, N-Terminal pro-brain natriuretic peptide; PFT, Pulmonary function test.

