### **12.6 OTHER SAFETY MEASURES**

#### 12.6.1 Electrocardiograms

All ECG assessments will be listed for all subjects. This listing will include the heart rate, the ECG interval from the beginning of QRS complex to end of the T wave (Q-T interval), the QT interval corrected for heart rate (QTc) (calculated using formulas by both Bazett and Fridericia as described in Section 8.4), the time between P wave and beginning of QRS complex in ECG (P-R interval), the electrocardiographic wave (QRS) duration, ECG results (Normal/Abnormal), whether there were clinically significant changes from Screening visit, whether abnormalities were present, and details and comments on any abnormalities. The ECG results at Baseline and changes at Week 16 will be descriptively summarized by treatment group. In addition, for QTc intervals calculated using both the Bazett and Fridericia methods, the number and percent of subjects with values  $\geq$ 500 msec and the number and percent of subjects with changes from Screening of <30 msec, 30 to <60 msec, and  $\geq$ 60 msec will be presented. Additionally, each abnormality will be summarized by number and percentage of subjects reporting at each visit by treatment group.

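### SAP Table 8-4 contradicts itself on whether a pre-dose SGRQ or ECG on Day 1 counts as Baseline, and SAP 12.6.1 takes QTc change categories from a Screening ECG that the protocol does not schedule

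*SAP*

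**What the plan says.** **Baseline window.** SAP 8.6, Table 8-4, gives ECG and SGRQ a Baseline target of Study Day 1 and the interval "Study Day ≤1 (prior to the date of the first dose". The Week 16 window for the same two assessments is any Study Day after 1. The Baseline rows for PFT, laboratory and NT-proBNP, for peak 6MWT, and for vital signs and oximetry have a different parenthesis: "Study Day $\leq 1$ (prior to the first dose". The note under the table defines "Study Day = (Assessment Date) - (First Dosing Date) +1". SAP 8 says how unplaced records are treated: "observations that do not fall within any predefined assessment window (and will, therefore, be excluded from summaries".

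**Timing in the protocol.** Protocol 3.1 states that "Day 1 is defined as the day the first dose of study drug is given", and the schedule in Protocol 3.2 puts both the Baseline visit and the combined Screening and Baseline visit on Study Day 1. Protocol 3.1 also lets the Baseline assessments be spread over the 48 hours before the first dose. Protocol 3.3.1.2 says "The SGRQ will be conducted at Baseline (prior to study drug", and for a combined visit it assigns the questionnaire to the Screening part. Protocol 3.3.2.3 has the ECG recorded "at Baseline (prior to study drug) and repeated at the Week 16 or ET Visit".

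**QTc reference.** SAP 12.6.1 summarises ECG results at Baseline and changes at Week 16, but counts "subjects with changes from Screening of <30 msec", 30 to <60 msec and ≥60 msec. It also lists an item on clinically significant change since the Screening visit.

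**The concern.** The analysis windows are to be derived from Table 8-4, so its wording is effectively the programming specification. In the ECG/SGRQ row, two programmers could each follow one half and obtain different analysis sets. The half that excludes the first-dose date removes valid pre-dose records taken on the protocol's nominal Baseline day.

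For SGRQ the effect would be direct. The ANCOVA needs a baseline score both to form the change and as the covariate, and SAP 8.3.2 and 10.3.2 allow no imputation. For ECG, the change summary would lose the same kind of record. Who stayed in these analyses would then depend on how sites scheduled the visit.

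The second defect concerns the QTc change categories, which are planned safety output. As worded, they refer to a visit at which no ECG is planned.

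**Working it through.** **Inputs.** The Study Day formula, target days and windows are from SAP Table 8-4. The treatment of records outside every window is from SAP 8. The visit day and the 48-hour allowance are from Protocol 3.1 and 3.2. The planned size of about 314 is from SAP 5.

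**The table's own figures.** An assessment on the first-dose date gives 0 + 1 = 1, the stated Baseline target. Week 16 falls 16 × 7 = 112 days after the first dose, and 112 + 1 = 113, the stated Week 16 target. The formula is therefore read correctly.

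**Each ECG/SGRQ condition applied by calendar date:**

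| Days from first dose | Study Day | ≤1 | Before first-dose date | Week 16 window (>1) |
|---|---|---|---|---|
| -2 | -1 | yes | yes | no |
| -1 | 0 | yes | yes | no |
| 0 | 1 | yes | no | no |
| +1 | 2 | no | no | yes |
| +112 | 113 | no | no | yes |

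The parenthesis amounts to Study Day ≤0, so the row's own target day can never satisfy it. Taken literally, it leaves a pre-dose record on Day 1 in neither window. Records from the one or two preceding calendar days qualify under both readings. With the wording of the other three Baseline rows, a pre-dose Day 1 record qualifies and no pre-dose record is left unplaced.

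**Number at risk.** On the literal reading, the number of SGRQ or ECG baselines lost is 314 × s, where s is the share of subjects whose assessment falls on the dosing date. The documents do not give s, and it may differ between the two assessments. For illustration only: s = 0 gives 0; s = 0.25 gives 78.5; s = 0.50 gives 157; s = 0.75 gives 235.5; s = 1 gives 314.

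**QTc reference visit.** The protocol synopsis, the schedule in 3.2 and section 3.3.2.3 place ECGs at Baseline and at Week 16 or early termination only. The Screening list in Protocol 7.1 contains no ECG. Protocol 7.3, for the combined visit, lists the ECG among the Baseline assessments. No scheduled recording therefore carries a Screening label. The summary of Baseline values and Week 16 changes does not use the Screening reference, and the count of QTc values at or above 500 msec needs no reference visit.

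**The case against.** The strongest reply is that the row does not plainly exclude Day 1. Its target day and its inequality both include that date; only the parenthesis excludes it, and reading the parenthesis as controlling makes the other two pointless. Other text favours the inclusive reading. Protocol 10.3.4 takes data collected before dosing as Baseline for safety measures, and SAP 8.6 announces changed windows only for Weeks 4, 8, 12 and 16. This stands: the row looks like a wording slip. A reader might infer that SGRQ and ECG baselines are lost outright under the plan. The documents support only a contradiction, with loss on one of two readings.

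A reader might also infer that most subjects would be lost. No document gives the same-day share, and baselines dated earlier within the 48 hours survive. The two assessments need not behave alike either: in a combined visit the SGRQ belongs to the Screening part and the ECG to the Baseline part, so an SGRQ dated before the dosing day is quite possible. This also stands.

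Nor does the Screening wording remove any ECG baseline. The Baseline ECG is scheduled; the category table merely points to the wrong visit.

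The blinded dry run in SAP 4 is meant to catch programming and data problems and might well reveal a depleted baseline column. That lowers the risk but is no reason to leave the text unresolved, since a partial loss is easier to miss. Finally, baselines are taken before dosing under blind, so there is no evident reason for imbalance between arms. The likely cost of the literal reading is precision, together with a subset shaped by site scheduling.

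**Conclusion.** Both defects are present in the text. The ECG/SGRQ Baseline row contradicts itself and departs from the other three Baseline rows. The QTc change categories refer to a visit with no scheduled ECG.

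The first causes loss only if the parenthesis is followed, and then only for baselines taken on the dosing date. Its size cannot be fixed from the documents. The second leaves three category counts without a scheduled reference value; it does not affect the change summary or the ≥500 msec count.

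The consequences are confined to the SGRQ analysis, which is exploratory and outside the testing hierarchy of SAP 8.4, and to descriptive ECG output. The primary and secondary endpoints are untouched. The point still merits correction, because these are stated rules that give a wrong or uncomputable result if followed literally, and because choosing between readings after unblinding would be a post hoc decision.

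**What to change.** Make these changes before database lock:

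- In Table 8-4, give the ECG/SGRQ Baseline row the same interval as the other three Baseline rows by dropping the reference to the date. Where no assessment time is collected, accept the nominal Baseline record, since Protocol 3.3.1.2 and 3.3.2.3 place both assessments before study drug. For SGRQ at a combined visit, that record may sit under the Screening part.
- In SAP 12.6.1, take the QTc change categories from Baseline.
- Check the listing item on clinically significant change since Screening against the eCRF before relabelling it. If the investigator records it with that reference, a new label in the SAP would misdescribe what was collected.

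The cost is two short wording edits and one eCRF check. No new data are needed.

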Abbreviations: ECG, electrocardiogram; NT-proBNP, N-terminal pro-brain natriuretic peptide; PFTs, pulmonary function tests; PH, pulmonary hypertension; SGRQ, St. George's Respiratory Questionnaire; 6MWT, 6-minute walk test; 6MWD, 6-minute walk distance; CT, computed topography; SpO₂, saturation of peripheral capillary oxygenation; HR, heart rate; eCRF, electronic case report form; FEV1, forced expiratory volume in 1 second; FVC, forced vital capacity; TLC, total lung capacity; DLCO, lung diffusion capacity; AE, adverse event; SAE, serious adverse event; 6MWD, 6-minute walk distance; ET, early termination

- ^a Screening Visit assessments can occur up to 30 days prior to the first dose of study drug. Baseline assessments can occur up to 48 hours prior to the first dose of study drug to allow for scheduling of all activities; however, the Baseline 6MWT must be performed prior to randomization. Screening and Baseline assessments may be combined if all entry criteria are satisfied within 48 hours prior to the first dose of study drug. Baseline PFTs, 6MWT, and CT scan (if a historical scan within 6 months is not available) assessments used to determine eligibility criteria must be performed prior to randomization. Sites should provide a completed Pre-Baseline review form to the Medical Monitor which will be reviewed, signed, and returned to the site prior to randomization.
- b The visit window for Week 4, Week 8, Week 12, Week 15, and Week 16 is ± 5 days. The Week 16 visit must occur at least 24 hours after the Week 15 visit.
- c For the Screening and Baseline Visits, the subject must be evaluated for and meet all inclusion/exclusion criteria.
- d Vital signs must be collected after 5 minutes of rest (seated); no other measurements or procedures should be performed during this 5-minute period. When possible, vital signs should be collected prior to the 6MWT. If vital signs cannot be obtained prior to the 6MWT then they should be obtained after recovery from the 6MWT.
- ^e Blood for NT-proBNP assessment must be drawn prior to conducting the 6MWT and will occur prior to randomization at Baseline (or as part of the Screening Visit assessment if the Screening and Baseline Visits are combined).
- f For subjects consenting to the optional biomarker sample.
- g For subjects consenting to the optional whole genome sequencing sample.
- h For females of childbearing potential.

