### Multiple Evaluations within the Same Analysis Window

After all the observations have been slotted based on the table above, if there are multiple valid observations for an assessment within an assigned analysis visit window, only 1 of these observations will be used for summary statistics and analyses. The observation to be used is determined using the following hierarchy (in decreasing order):

- The observation closest to the target study day
- The later observation if 2 observations are equally close to the target study day

For missing values where the LOCF algorithm is applied, it is always the last valid observation on treatment carried forward, even though this might not be the observation obtained by the above hierarchy and used in the summaries by visit window.

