# 10.3.4 Change in DSP

The DSP will be calculated, and DSP results will be included in the data listing for pulse oximetry. DSP values and their respective changes from Baseline to Week 16 will be summarized by treatment group. The difference between treatment groups for the change from Baseline to Week 16 will be tested using analysis of covariance with change from Baseline in DSP as the dependent variable, treatment as a fixed effect, and Baseline DSP measure as the covariate. The analyses will be based on the observed data with no imputation.

The pseudo SAS code is as follows:

proc glm; class treatment; model DSP\_C=Treatment DSP\_B; run;

where DSP\_C is the change from Baseline to Week 16 in DSP (m%) and DSP\_B is DSP at Baseline.

In addition, the DSP at Week 4, Week 8, and Week 12 will each be analyzed in the same way as the DSP at Week 16.

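### In SAP Table 8-4 the Week 16 interval for vital signs and pulse oximetry does not exclude Week 15 (trough-visit) records

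*SAP*

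**What the plan says.** SAP Section 8.6, Table 8-4, treats the two kinds of walk separately. Peak 6MWT and trough 6MWT have their own blocks, and the trough block contains Week 15 only. Vital signs and pulse oximetry share a single block that holds both visits:

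- Week 15 (target Day 106) is assigned by label: "Nominal study visit and at least 24 hours prior to Week 16 6MWT or no Week 16 visit". The text above the table agrees: "The nominal study visit identified as Week 15 in the eCRF will be used for the Week 15 visit".
- Week 16 (target Day 113) is any study day above 99. It has no upper limit and no condition on the visit label.

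Study day is defined under the table: "Study Day = (Assessment Date) - (First Dosing Date) +1".

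If a window holds several records, the SAP keeps one. The first criterion is "The observation closest to the target study day"; the tie-break is "The later observation if 2 observations are equally close to the target study day".

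DSP has no row in Table 8-4. Section 8.5 defines it as walk distance times the lowest SpO2 during the walk. Section 10.3.4 says that "DSP results will be included in the data listing for pulse oximetry", and analyses DSP at Week 16 and also at Weeks 4, 8 and 12, using observed data only.

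**The concern.** Week 15 and Week 16 are measured at different points after dosing. Under Protocol Section 3.3.1.1.3 the Week 15 walk takes place at least 4 hours after a dose and the Week 16 walk 10 to 60 minutes after one. Pulse oximetry is taken just before, during and just after each walk (Protocol Section 3.3.2.6.1), so SpO2 carries the same contrast.

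The SAP keeps trough walk distance out of Week 16 by giving it a separate block, but has no such barrier for the SpO2 recorded during that walk. A programmer who codes Table 8-4 literally would let a Week 15 record compete for the Week 16 slot. If it won, one trough measurement could appear at both Week 15 and Week 16, and the Week 16 oxygenation table would mix two exposures. Oxygenation is a named safety endpoint, summarised by visit with changes from Baseline and threshold categories (SAP Section 12.3).

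**Working it through.** **Inputs**

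- Target days 106 and 113, the Week 16 interval above Day 99 and the selection rules: SAP Section 8.6.
- Visit windows: "The visit window for Week 4, Week 8, Week 12, Week 15, and Week 16 is ± 5 days" (Protocol Section 3.2, footnote b).
- Minimum gap: "The Week 16 visit must occur at least 24 hours after the Week 15 visit" (same footnote), taken here as at least one calendar day.

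**Reproducing the plan's days.** Target day = 7 × week + 1. Week 15: 7 × 15 + 1 = 106. Week 16: 7 × 16 + 1 = 113. The cut between Weeks 12 and 16 is the midpoint of their targets: (85 + 113)/2 = 99. All agree with Table 8-4.

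**Overlap.** Week 15 in window is 106 ± 5 = Days 101 to 111; Week 16 in window is 113 ± 5 = Days 108 to 118. The earliest in-window Week 15 day, 101, is already above 99, so every in-window Week 15 record also meets the Week 16 interval. A nominal Week 15 visit fails it only if held on Day 99 or earlier, which is 106 − 99 = 7 or more days early and outside the protocol window.

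**Number of day pairs with Week 16 later than Week 15.**

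- Week 15 on Days 101 to 107: 7 × 11 = 77 pairs.
- Week 15 on Days 108, 109, 110 and 111: 10 + 9 + 8 + 7 = 34 pairs.
- Total: 77 + 34 = 111.

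**Which record is selected for Week 16.** The Week 15 record wins when its distance from Day 113 is strictly smaller:

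| Week 15 day | Week 16 day | Week 15 distance | Week 16 distance |
|---|---|---|---|
| 109 | 118 | 4 | 5 |
| 110 | 117 | 3 | 4 |
| 110 | 118 | 3 | 5 |
| 111 | 116 | 2 | 3 |
| 111 | 117 | 2 | 4 |
| 111 | 118 | 2 | 5 |

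That is 6 of 111 pairs. Four pairs tie (108/118, 109/117, 110/116, 111/115) and go to the later record, the true Week 16 visit. In all six pairs both visits are at least 3 days late (109 − 106 = 3; 116 − 113 = 3). With both visits on target (106/113) the right record is chosen. A Day 106 record is 7 days from target, so it wins only if Week 16 falls on Day 121 or later.

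**No Week 16 visit.** The Week 15 record keeps its Week 15 slot, because the row provides for this case. Read literally it also fills Week 16, unless another record after Day 99, such as an early termination visit, lies closer to Day 113.

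**With nominal Week 15 records excluded from the Week 16 interval.** The 6 pairs become 0 of 111, and a subject with no record after Day 99 other than Week 15 has no Week 16 value.

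**The case against.** The strongest reply is that the SAP already assigns these records. It says the nominal Week 15 visit serves Week 15, and that the other windows were widened to place discontinuation visits and off-schedule visits, which a scheduled Week 15 visit is not. The remaining post-Baseline intervals in the block do not overlap, and the nearest-day rule applies after slotting, which suggests one window per record. The Week 15 row also covers the case of no Week 16 visit. This reading is plausible and may be what was intended. But the SAP does not say that a nominal Week 15 record serves Week 15 only, and the same section says windows are derived from Table 8-4, where the record meets both rows. Two programmers could code it differently.

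Other parts of the reply stand and limit the point:

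- Vital signs are not timed to dosing; they are taken before the walk or after recovery from it (Protocol Section 3.3.2.2). The exposure argument is therefore mainly about SpO2.
- Protocol Section 10.3.4 plans no inferential analysis of vital signs or oxygenation.
- The group without a Week 16 visit is probably small. Subjects who stop study drug before Week 15 need not attend that visit (Protocol Section 7.5), and those who stop after it should have a termination visit, which may fall closer to Day 113.

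A reader might infer that trough values enter the Week 16 DSP test. The documents do not establish that. Sharing a listing with pulse oximetry sets no analysis window, and DSP is analysed at Weeks 4, 8, 12 and 16, which is the peak-walk schedule. A peak-only DSP looks intended; the gap is that no rule says so, and none requires the distance and the SpO2 to come from the same walk.

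**Conclusion.** The point holds as a minor gap in wording. Table 8-4 lets any in-window Week 15 vital-sign or pulse-oximetry record qualify for Week 16 as well, and the selection rule does not always remove it. A trough-visit SpO2 can be reported as Week 16 when both visits run late, or when there is no Week 16 visit and no closer record after Day 99. This assumes a literal coding of the table, both visits inside the protocol windows in the first case, and the 24-hour gap counted as one calendar day.

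Three stronger conclusions are tempting and should not be drawn:

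- That about 5% of subjects are affected (6/111). The documents give no distribution of visit days, so the fraction counts possibilities and estimates no rate.
- That every subject without a Week 16 visit receives a trough value. Another record after Day 99 may be closer to Day 113.
- That the main efficacy results are at risk. Peak and trough 6MWD have separate blocks and NT-proBNP is not scheduled at Week 15, so the primary and secondary endpoints are untouched.

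The exploratory DSP test is exposed only if DSP is programmed from the pulse-oximetry row.

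**What to change.** In Table 8-4, restate the Week 16 interval for vital signs and pulse oximetry as study day above 99, excluding records from the nominal Week 15 visit. Add a sentence that DSP at each visit uses the distance and the lowest SpO2 from the same peak 6MWT selected for that visit.

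The cost is one phrase, one sentence and a line of code, best settled before unblinding. The downside is a few more missing Week 16 cells, for subjects whose only record after Day 99 is the trough visit. If the authors already meant to reserve Week 15 records for Week 15, the change only records that intention.
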